### Participants

Older adults (> 55 years) will be recruited from the University of Illinois Hospital Geriatric Clinic and flyers in nearby independent living senior centers and grocery stores. We expect ten older adults participated in the study after obtaining a written informed consent.

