### Research Design

This study will be a single arm pre-post research design consisting of 4 weeks of DT exergaming sessions. Baseline (at week 0) and post-testing (at 5th week) outcome measures will be collected.

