## Assessments

Volitional balance control task: The limits of stability (LOS) test via Balance Master (Equitest® Neurocom) (18) will be administered. Participants will be secured in a safety harness and asked to stand on the force platform of the Balance Master (Figure 1). Participants will be instructed to lean their body either in the forward, backward, left, or right direction to move their center of gravity (COG) projection shown on a screen to the desired direction without losing balance, stepping, or reaching for assistance.

[figure not shown]

Figure 1

Represents a picture of an individual performing the limits of stability test on Balance Master (Equitest® Neurocom) in the forward direction

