## Statistical analyses

Statistical analyses will be performed using SPSS version 24, Chicago, IL, USA. For MXE in each volitional balance control task direction (i.e., forward, backward, left, and right), 2 x 2 repeated measures analysis of variance (ANOVA) will be performed to examine the time (pre- to post-training) and task (single vs. interference task) differences on with follow-up post-hoc tests. Similarly, four repeated measures ANOVA for accuracy (cognitive) in ACT and LNS will be performed. Paired t-test will be conducted for NIH toolbox measures. Refer supplementary material section for detail

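### The planned 2 x 2 repeated-measures ANOVAs drop a participant from an outcome if one of four cells is missing; a mixed model with matching error terms keeps the data.

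*Combined protocol and SAP*

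**What the plan says.** The Participants section gives the expected size: "We expect ten older adults participated in the study". Research Design sets two measurement times: "Baseline (at week 0) and post-testing (at 5th week) outcome measures will be collected".

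For maximum excursion (MXE), Statistical analyses says that "2 x 2 repeated measures analysis of variance (ANOVA) will be performed" in each of four directions, with time and task (single or interference) as the two within-person factors. For the cognitive outcomes it says that "four repeated measures ANOVA for accuracy (cognitive) in ACT and LNS will be performed". The software is SPSS 24.

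The text supplied contains no missing-data rule, analysis set or dropout allowance, and no mixed model. Statistical analyses refers to a supplement for detail; that supplement is not part of the text.

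The Assessments section tells participants to lean "without losing balance, stepping, or reaching for assistance". Neither that section nor Outcome measures says how a trial is scored when this is not achieved.

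**The concern.** Repeated-measures ANOVA, as normally run in SPSS, works on complete rows. Each MXE analysis needs four values per person: two visits by two task conditions. A person with three valid values and one missing contributes nothing to that outcome. The deletion acts outcome by outcome, so the four directional results could rest on different subsets of the ten.

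The main stake is precision. With ten people, each deletion visibly widens the interval. There is also a possible bias, because complete-case results can shift when missingness is related to performance.

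**Working it through.** **Inputs.** From the document: n = 10, two visits, two task conditions, hence four cells per person. Assumed, because the document gives no figures: two-sided 95% intervals, the missingness rates and the covariance. The plan states no power or precision figure, so there is nothing to reproduce first.

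**1. Expected complete participants.** With independent missingness p per cell, the expected number is 10 x (1 - p)^4, and the chance that all ten are complete is (1 - p)^40.

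- p = 2.5%: 10 x 0.975^4 = 9.0; all complete 36%
- p = 5%: 10 x 0.95^4 = 8.15; all complete 13%
- p = 10%: 10 x 0.90^4 = 6.56; all complete 1.5%

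**2. What losing people costs.** The 95% half-width for a within-person contrast, in SDs of that contrast, is t(0.975, n - 1)/sqrt(n): 0.715 at n = 10, 0.836 at n = 8 and 0.925 at n = 7. Going from ten to eight widens the interval by 0.836/0.715 - 1 = 17%. This compares ten complete people with eight; it is not the gain from a mixed model.

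**3. Listwise deletion against all available data.** Assume total variance 1, with shares 0.5 participant, 0.1 participant-by-time, 0.1 participant-by-task and 0.3 residual. Correlations are then 0.6 between cells sharing a visit or a task, and 0.5 otherwise. Let V be this 4 x 4 matrix, c the contrast, k the number of incomplete people and Z the rows they still have.

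- Listwise variance: c'Vc/(10 - k). For time, c'Vc = 2 x 0.1 + 0.3 = 0.5.
- All-available variance: c'[(10 - k)V^-1 + kZ'(ZVZ')^-1 Z]^-1 c.

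Time-effect standard errors, the first two columns relative to ten complete people:

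| Pattern | k | Listwise | All available | Ratio |
|---|---|---|---|---|
| One cell missing | 1 | 1.054 | 1.014 | 1.039 |
| | 2 | 1.118 | 1.032 | 1.083 |
| | 3 | 1.195 | 1.054 | 1.134 |
| Whole post visit missing | 1 | 1.054 | 1.046 | 1.008 |
| | 2 | 1.118 | 1.100 | 1.016 |
| | 3 | 1.195 | 1.167 | 1.024 |

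For the interaction with one cell missing, the ratios are 1.030, 1.062 and 1.098.

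*Sensitivity.* With one common correlation of 0.3 to 0.7, the one-cell time ratios are about 1.036 (k = 1), 1.075 to 1.079 (k = 2) and 1.120 to 1.126 (k = 3). With the whole post visit missing, the k = 3 ratio runs from sqrt(1.429/1.391) = 1.014 at correlation 0.7 to sqrt(1.429/1.313) = 1.043 at 0.3. These figures treat the covariance as known; estimating it from ten people would reduce the gain somewhat.

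**4. Bias.** This was simulated with n = 10, about 1,500 runs, correlation 0.5 and true task effect -5, all assumed.

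- Missingness depends on the observed single-task score: ANOVA averaged -5.95, mixed model -5.04.
- Missingness depends on the unseen interference score: ANOVA -4.07, mixed model -3.71. At correlation 0.7: -4.44 and -4.18.

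**5. Which mixed model.** With the step 3 shares and complete data, the expected error mean squares are 0.3 + 2 x 0.1 = 0.5 for time, 0.5 for task and 0.3 for the interaction, each on 9 df. A random-intercept model pools them on 27 df: (0.5 + 0.5 + 0.3)/3 = 0.433. That is too small for time and task and too large for the interaction. Simulated type I error at a nominal 5% is about 6.7% for time and task and 2% for the interaction, against about 5% for the planned ANOVA. With a participant-by-time share of 0.2 and no participant-by-task share, time reaches 12%.

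**The case against.** The strongest reply is that the harm is conditional. With complete data the ANOVA is valid and nothing is lost, and this is a ten-person study with supervised sessions. The missingness rates and variance shares are assumptions. The supplement may contain a missing-data rule. If the likely loss is dropout before week 5, a mixed model recovers almost nothing for the time effect. All of this stands, and it limits the size of the point.

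A reader might also infer that people who step or reach for support in interference trials will be deleted, so that interference performance is biased upward, and that a mixed model would prevent this. The document does not support the first step. The wording in Assessments is an instruction to participants, not a scoring or exclusion rule. A poor trial may still yield a low MXE, and accuracy can be computed from the responses given. Nor does the second step follow: where missingness depends on the unseen interference score, the mixed model was slightly further from the truth than the ANOVA in the simulation.

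What survives is narrower. The named method discards valid data whenever a single cell is absent, and the text gives no rule for that case.

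**Conclusion.** The point holds as a conditional loss of precision that is cheap to avoid. For one to three people each lacking an isolated cell, listwise deletion inflates the time-effect standard error by about 4% to 13%, and this depends little on the assumed correlation. For a missed post visit the figure is about 1% to 2% under the stated shares and at most about 4% over the correlations tried. With complete data it is zero.

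Protection against bias extends only to missingness explained by observed data. Whether failed trials become missing cells at all is not stated, so no claim about the direction or size of bias in this study is justified.

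**What to change.** For each outcome now assigned a repeated-measures ANOVA, specify a linear mixed model in SPSS:

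- **Model:** fixed time, task and time x task; REML; Satterthwaite degrees of freedom.
- **Covariance:** unstructured within participant, or random effects for participant, participant-by-time and participant-by-task. With complete data the tests then agree with the planned ANOVA (for the random-effects form, provided no variance component is estimated at zero). Do not use a random intercept alone.
- **Fallback:** state in advance that if the unstructured covariance is unstable at n = 10, the simpler structure is used, keeping the participant-by-time and participant-by-task terms.
- **Analysis set:** every participant with any data on the outcome.
- **Reporting:** missing or unusable cells by visit and task, with reasons.
- **Sensitivity analysis:** assign a poor score to any interference trial missing because of failure.

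The cost is a change of wording and slightly more analysis work. It needs no extra data, visits or software. The main downside is possible instability of the covariance estimate with ten people, which the fallback addresses.

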## Interference test

The LOS test (all directions) will be performed along with both cognitive tasks mentioned above. Participants will began responding to the cognitive cues followed by the LOS task.

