## Outcome measures

Volitional balance control and interference task: Single task (task when performed alone) and performance during interference task was quantified by the movement stability measurement of maximum excursion (MXE, expressed in percentage), which is the maximum ability to shift one’s COG toward the theoretical limit in the desired direction. Higher values indicate better performance.

Cognitive and interference task: Accuracy  $[(\text{Correct responses}) / (\text{Total responses}) * 100]$  was calculated during single and interference task.

NIH toolbox: Speed (m/sec) for 4-meter gait test and distance covered in 2-minute walk test for endurance will be computed. Number of correct responses for list sort memory test and accuracy for the remainder tests was included for analysis.

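### Does it matter that the analysis section does not say how the two dual-task conditions enter its two-level task factor, or which analyses its four accuracy ANOVAs are?

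*Combined protocol and SAP*

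**What the plan says.** For balance, the Statistical analyses section specifies "For MXE in each volitional balance control task direction (i.e., forward, backward, left, and right), 2 x 2 repeated measures analysis of variance" to "examine the time (pre- to post-training) and task (single vs. interference task) differences", "with follow-up post-hoc tests". Task has two levels, single and interference.

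For cognition, the same section continues: "Similarly, four repeated measures ANOVA for accuracy (cognitive) in ACT and LNS will be performed".

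The Interference test section states: "The LOS test (all directions) will be performed along with both cognitive tasks mentioned above". Under Outcome measures, accuracy is a percentage of correct responses that "was calculated during single and interference task"; neither the cognitive task nor the LOS direction is named there.

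The Statistical analyses section ends by deferring to another source: "Refer supplementary material section for detail". That supplement is not part of the supplied text. The Participants section gives the planned size: "We expect ten older adults participated in the study".

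**The concern.** Set against the data to be collected, the model looks one condition short. Each direction yields three MXE conditions at each visit (LOS alone, LOS with ACT, LOS with LNS), and the task factor has room for two. The reader is not told whether ACT and LNS are averaged, analysed separately, or represented by one of them. The accuracy sentence has a similar problem: two cognitive tasks and four directions make eight series, and the stated number is four.

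The time-by-task interaction is the test of whether training changes dual-task interference. Two analysts could compute different interactions from the same ten people and both claim to follow the plan. If the choice between ACT and LNS were made after seeing both results, the error rate would exceed its nominal level. No primary contrast is named that would settle which result counts.

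**Working it through.** **Inputs from the documents.** Directions: 4 (Statistical analyses). Cognitive tasks: 2 (Cognitive task). Visits: 2 (Research Design). Participants: 10 (Participants). Task levels in the model: 2 (Statistical analyses). The documents give no alpha, standard deviation, correlation or effect size.

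**Cells per direction, MXE.** Collected: 2 visits x 3 conditions = 6. In one 2 x 2 model: 4. The mismatch is real. It disappears if the two interference conditions are averaged (one model per direction) or taken in turn against the single task (two models per direction).

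**The stated figure of four.**
- One per direction, ACT and LNS combined: 4. Matches.
- Four for each cognitive task: 4 x 2 = 8, which is the full set of task-by-direction series. Matches.
- One per cognitive task, ignoring direction: 2. Does not match.

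Two readings fit, so the number is ambiguous but not wrong.

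**Total ANOVAs.**

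| | Accuracy: four in total | Accuracy: four per task |
|---|---|---|
| MXE: one per direction (4) | 4 + 4 = 8 | 4 + 8 = 12 |
| MXE: one per direction and task (8) | 8 + 4 = 12 | 8 + 8 = 16 |

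Sixteen is arguably the most natural reading, since it treats both outcomes alike and merges no different tests. The text does not fix it.

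**Error rate of one reading.** With one value per cell, the 2 x 2 interaction is a paired t-test with 9 degrees of freedom on the difference between the interference change and the single-task change. That holds for ACT alone, LNS alone or their average. I simulated 60,000 null data sets with assumed two-sided 5% tests, normal changes of unit variance, a single-interference correlation of 0.5 and an ACT-LNS correlation from 0.2 to 0.9. Each reading fixed in advance rejected in about 5% of data sets. Picking whichever of ACT and LNS was significant gave about 9.7% at a correlation of 0.2 and 7.1% at 0.9. The ceiling is 2 x 5% = 10%.

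**Power of the readings.** This assumes a 1.0 SD interaction effect and the same correlations. The SD of a separate contrast is sqrt(1 + 1 - 2 x 0.5) = 1. The SD of the averaged contrast is sqrt(1 + (1 + r)/2 - 2 x 0.5), where r is the ACT-LNS correlation: 0.775 at r = 0.2 and 0.975 at r = 0.9. From the noncentral t:
- Effect equal under both tasks: 80% for a separate model; 95% (r = 0.2) to 82% (r = 0.9) averaged.
- Effect under one task only: 80% for that task; 45% to 31% averaged.

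The better choice reverses with the response pattern, and the documents do not say which pattern is expected.

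**The case for a change.** The strongest case for a change is that it costs only a few lines. A list of the ANOVAs by outcome, cognitive task and direction would remove the ambiguity without new data. The gap is also wider than the count alone shows. The Cognitive task section describes ACT and LNS with no LOS direction, so a per-direction accuracy analysis would seem to reuse one single-task value four times. With ten participants and no named primary contrast, an unstated choice leaves room for selection. Over four independent directions, even one fixed contrast per direction gives 1 - 0.95^4 = 18.5% for at least one false positive, and choosing the cognitive task afterwards raises that further.

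Part of this stands. The supplied text does not give the mapping, and a list would help a reader. The rest does not carry a change. The 18.5% arises under a fully specified reading as well, so it describes multiplicity and not this gap. The added inflation requires reporting the more favourable of ACT and LNS after the fact, whereas running both and reporting both is equally consistent with the text. Naming a primary contrast, or labelling everything exploratory, is a separate request about policy. It does not correct the model, and this is a small single-arm study that states no decision threshold.

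**Conclusion.** No change follows. The supplied text leaves two points open: how LOS with ACT and LOS with LNS enter the two-level task factor, and whether the four accuracy ANOVAs are a total or a number per task. The range is 8, 12 or 16 ANOVAs. An analyst can fill this sensibly by running each cognitive task separately in each direction, or by averaging the two. Each option is valid if fixed in advance, and the assumed power figures show no option that is better throughout. The section also points to a supplement for detail at exactly this place, so the mapping may already be written down.

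The counts rest on the documents alone. The error-rate and power figures rest on an assumed 5% level, assumed correlations and an assumed effect; they illustrate the point and are not evidence of a fault in the plan. The conclusion would change only if the supplement were silent and there were signs that the cognitive task had been selected after the results were known. Nothing supplied suggests either.
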